## Study Definitions Page

Adverse Event	Any untoward or unfavorable medical occurrence associated with the subject's participation in the research, whether or not considered related to the subject's participation in the research (Section 8.2.1).
Biliary Complications	Incidence of biliary complications including any of the following: 
 
• Biliary stricture requiring stenting
 
• Other evidence of biliary obstruction
 
• Cholangitis
 

Enrollment	The signing of informed consent (Section 3.1.1).
Liver Graft Loss	The incidence of any of the following: 
 
• Re-transplantation
 
• Re-listing for transplantation
 
• Participant death with a non-functioning graft
 

Normal and stable graft function	
Baseline (Values collected at screening):
 
Liver transplant recipients: Liver function tests (ALT, GGT) both less than or equal to the upper limit of normal (ULN).
 
Kidney transplant recipients: Serum creatinine value correspond to an estimated GFR > 45 ml/min/1.73 m^2.
 
Post-Baseline
 
Liver function tests (ALT, GGT) (for liver transplant recipients) that have not increased more than 50% above the participant's baseline values or serum creatinine (for kidney transplant recipients) that have not increased more than 25% above the participant's baseline values, and these tests were collected in the absence of confounding factors.

Operational Tolerance	Participants must meet all of these criteria for at least 52 weeks after the last documented dose of immunosuppressive medication: 
 
1. Absence of rejection (biopsy-proven or clinical rejection)
 
2. Maintenance off immunosuppressive medication
 
3. Normal and/or stable allograft function
 

Primary Endpoint Adjudication Committee	The Primary Endpoint Adjudication Committee is comprised of the Study Protocol Chair/ITN Clinical Trial Physician, NIH Medical Monitor, a subject matter expert, and Statistician. The Committee will review the participant's clinical history to determine whether the participant is operationally tolerant.
Renal Function	Estimated GFR calculated for adults by CKD-EPI and for pediatric participants (<18 years) by both CKD-EPI and modified Schwartz formulae  .

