### 9.2 ANALYSIS PLAN

#### 9.2.1 Primary Endpoint

The primary endpoint is defined in section 3.3.2.

A confounding factor may prevent measurement of normal and stable allograft function. Participants who return to normal and stable allograft function after resolution of the confounding factor and who otherwise meet the primary endpoint criteria will be adjudicated by a Primary Endpoint Adjudication Committee (see Study Definitions).

The primary endpoint will be analyzed using Kaplan-Meier survival estimates and associated two-sided 95% confidence intervals, using a delayed-entry model controlling for left-truncation of survival times through adjusting for the time from achieving operational tolerance to the time of study enrollment. A participant will be considered to have lost operational tolerance if they experience rejection, have loss of stable allograft function (in the absence of confounding factors), or restart immunosuppression. The date of loss of operational tolerance will be the first date on which the subject meets any of the criteria for loss of operational tolerance. Subjects lost to follow-up will be censored at the time of occurrence of the event causing their loss to follow-up.

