### **7.2.2. Primary Analysis of the Primary Endpoint**

The primary endpoint will be analyzed using Kaplan-Meier survival estimates and associated two-sided 95% confidence interval, using a delayed-entry model controlling for left-truncation of survival times through adjusting for the time from achieving operational tolerance to the time of study enrollment.

A participant will be considered to have lost operational tolerance if they experience rejection, have loss of stable allograft function (in the absence of confounding factors), or restart immunosuppression. The date of loss of operational tolerance (end date of operational tolerance) will be the first date on which the subject meets any of the criteria for loss of operational tolerance. Specifically,

- If tolerance is lost due to rejection, the date will equal the date of the biopsy.
- If tolerance is lost due to restarting immunosuppression, the date will equal the date of the first immunosuppression medication dosage.
- If tolerance is lost due to abnormal allograft function, the date will equal the first recorded abnormal lab date.

The time to loss of operational tolerance for all participants will be evaluated relative to time zero. Time zero will be considered 52 weeks from the participant's last documented dose of immunosuppression and in the absence of rejection or evidence for loss of normal and stable graft function since that last dose. If the exact date of the last dose is not known, the date will be imputed to the 15th of the month when the day is missing, and July 1st when both day and month are missing. The year must be known.

$$\begin{aligned} & \text{time to loss of operational tolerance} \\ & \quad = \text{end date of operational tolerance} - \text{start date of operational tolerance} \end{aligned}$$

Subjects lost to death, voluntary withdrawal or lost to follow-up will be censored at the time of occurrence of these events. Subjects who were followed until study closure (24MAR2020) without losing tolerance will be censored at the time of their most recent data point.

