**Table 7-2 Table of Secondary Endpoints and Analysis Methods**

Secondary Endpoint	Method	Population
Time to development of de novo anti-HLA antibody or DSA.	The time to the first de novo anti-HLA antibody or DSA be expressed in days from time zero.  Kaplan-Meier survival estimate and associated two-sided 95% confidence interval, using a delayed-entry model controlling for left-truncation of survival times through adjusting for the time from achieving operational tolerance to the time of study enrollment.	Analysis sample defined in Section 4
Time to the first episode of biopsy-proven or clinical acute rejection, steroid resistant rejection and chronic rejection.	The time to the first episode of biopsy-proven or clinical acute rejection, steroid resistant rejection or chronic rejection be expressed in days from time zero.  Kaplan-Meier survival estimate and associated two-sided 95% confidence interval, using a delayed-entry model controlling for left-truncation of survival times through adjusting for the time from achieving operational tolerance to the time of study enrollment.	Analysis sample defined in Section 4
Time to graft loss, not including death with functioning graft.	The time graft loss, not including death with functioning graft, will be expressed in days from time zero.  Kaplan-Meier survival estimate and associated two-sided 95% confidence interval, using a delayed-entry model controlling for left-truncation of survival	Analysis sample defined in Section 4

times through adjusting for the time from achieving operational tolerance to the time of study enrollment.

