## 7.5. Other Endpoints

The following endpoints will be examined in an exploratory nature. All analyses will be dependent upon the availability of the data.

Exploratory Endpoint	Method	Population
Time to all-cause mortality	
The time to all-cause mortality will be expressed in days from time zero.
 
Kaplan-Meier survival estimate and associated two-sided 95% confidence interval, using a delayed-entry model controlling for left-truncation of survival times through adjusting for the time from achieving operational tolerance to the time of study enrollment.
	Analysis sample defined in Section 4
Changes in renal function (defined as estimated GFR (eGFR) calculated by CKD-EPI over time in renal transplant recipients	
eGFR will be calculated using the CKD-EPI equation:
 $\text{GFR} = 141 * \min(\text{Scr}/\kappa, 1)^\alpha * \max(\text{Scr}/\kappa, 1)^{-1.209} * 0.993^{\text{Age}} * 1.018 \text{ [if female]} * 1.159 \text{ [if black]}$ 
Scr: serum creatinine (mg/dL)  <math>\kappa</math>: 0.7 for females and 0.9 for males  <math>\alpha</math>: -0.329 for females and -0.411 for males
 
All available eGFR will be displayed graphically over time in two separate ways—as absolute values and as percent change from baseline.
	Kidney transplant recipients of the analysis sample defined in Section 4
Changes in liver tests (ALT, GGT) over time in liver transplant recipients	All available ALT and GGT will be displayed graphically over time in two separate ways—as absolute values and as percent change from baseline.	Liver transplant recipients of the analysis sample defined in Section 4

Time to incidence of biliary complications in liver transplant recipients	The time to the earliest of biliary stricture requiring stenting, biliary obstruction, or cholangitis will be expressed in days from time zero.  Kaplan-Meier survival estimate and associated two-sided 95% confidence interval, using a delayed-entry model controlling for left-truncation of survival times through adjusting for the time from achieving operational tolerance to the time of study enrollment.	Liver transplant recipients of the analysis sample defined in Section 4

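### Deaths are censored in the loss-of-tolerance curve, and by implication in the graft-loss curve, so reading the complement as the proportion of recipients affected would overstate loss; a cumulative incidence estimate should stand beside it

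*SAP*

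**What the plan says.** SAP 7.2.2 sets the estimator: "The primary endpoint will be analyzed using Kaplan-Meier survival estimates and associated two-sided 95% confidence interval, using a delayed-entry model". The events are given there as follows: "A participant will be considered to have lost operational tolerance if they experience rejection, have loss of stable allograft function", or restarting immunosuppression. Death is not among them. The same section then says: "Subjects lost to death, voluntary withdrawal or lost to follow-up will be censored at the time of occurrence of these events". Protocol 9.2.1 has a narrower rule that does not mention death: "Subjects lost to follow-up will be censored at the time of occurrence of the event causing their loss to follow-up".

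For graft loss, SAP Table 7-2 uses the same delayed-entry Kaplan-Meier method, with the rule "The time graft loss, not including death with functioning graft, will be expressed in days from time zero". The table does not say what happens to a participant who dies with a working graft. Since that death is not an event, a Kaplan-Meier analysis can only censor it. One kind of death does count: the Protocol's definition of liver graft loss includes "Participant death with a non-functioning graft".

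Mortality has its own exploratory analysis in SAP 7.5: "The time to all-cause mortality will be expressed in days from time zero". SAP 8.3 plans a listing of deaths with time and cause. Neither document mentions competing risks or cumulative incidence, and SAP 7.2.3, on sensitivity analyses of the primary endpoint, is a heading with no text under it.

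**The concern.** A participant who withdraws while tolerant may still lose tolerance later, unobserved. A participant who dies while tolerant cannot. Censoring treats the two alike: in effect it assigns to the dead the later loss experience of those still under observation. The resulting curve answers the question of how long tolerance would last if nobody died.

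The third secondary objective (Protocol 2.2) is to assess how durable tolerance is over time. Physicians and patients will naturally take that as the fraction of tolerant recipients who stay tolerant or lose tolerance. If one minus the curve is quoted as that fraction, it is too high. The excess grows with the number of deaths and with time since time zero. Nothing in the SAP labels the primary curve as death-censored, or states the independence assumption that its death-removed reading needs.

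**Working it through.** **Nothing to reproduce.** The documents contain no sample-size calculation, event count, loss rate or death rate. The accrual figure of about 70 (Protocol 9.3) is an estimate only. All rates below are therefore assumptions, shown over a range.

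**Direction.** Let Y be the number at risk just before a loss event; with delayed entry, only participants already enrolled count. At each loss event:
- one minus Kaplan-Meier rises by S(loss only) × 1/Y;
- the Aalen-Johansen cumulative incidence rises by S(loss or death) × 1/Y.

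S(loss or death) takes an extra downward step at each death, so it is never above S(loss only). The complement of the Kaplan-Meier is therefore never below the cumulative incidence on the same data, and is above it once a death precedes a later loss. Left truncation does not change this, because both estimators use the same Y.

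**Size, constant yearly hazards.** With loss hazard l, death hazard d and t years after time zero:
- one minus Kaplan-Meier (death censored) = 1 − exp(−l·t)
- cumulative incidence of loss = l/(l+d) × [1 − exp(−(l+d)·t)]

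Example with l = 0.05, d = 0.02, t = 10:
- 1 − exp(−0.5) = 39.3%
- (0.05/0.07) × [1 − exp(−0.7)] = 36.0%
- difference 3.4 points

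The full range follows, as 1−KM vs cumulative incidence in %, with the difference in points in brackets. Differences are taken before rounding.

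| Loss/y | Death/y | 5 years | 10 years |
|---|---|---|---|
| 1% | 0.5% | 4.9 vs 4.8 (0.1) | 9.5 vs 9.3 (0.2) |
| 1% | 1% | 4.9 vs 4.8 (0.1) | 9.5 vs 9.1 (0.5) |
| 1% | 2% | 4.9 vs 4.6 (0.2) | 9.5 vs 8.6 (0.9) |
| 1% | 4% | 4.9 vs 4.4 (0.5) | 9.5 vs 7.9 (1.6) |
| 3% | 0.5% | 13.9 vs 13.8 (0.2) | 25.9 vs 25.3 (0.6) |
| 3% | 1% | 13.9 vs 13.6 (0.3) | 25.9 vs 24.7 (1.2) |
| 3% | 2% | 13.9 vs 13.3 (0.7) | 25.9 vs 23.6 (2.3) |
| 3% | 4% | 13.9 vs 12.7 (1.3) | 25.9 vs 21.6 (4.3) |
| 5% | 0.5% | 22.1 vs 21.9 (0.3) | 39.3 vs 38.5 (0.9) |
| 5% | 1% | 22.1 vs 21.6 (0.5) | 39.3 vs 37.6 (1.7) |
| 5% | 2% | 22.1 vs 21.1 (1.0) | 39.3 vs 36.0 (3.4) |
| 5% | 4% | 22.1 vs 20.1 (2.0) | 39.3 vs 33.0 (6.4) |

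**Against sampling error.** A simulation used 70 participants, entry uniform over 0 to 10 years after time zero, follow-up uniform over 1 to 5 years, and 2,000 runs (entry and follow-up patterns also assumed). Mean results at 10 years with loss at 5% per year:
- death 1% per year (about 2 deaths): 38.8% vs 37.2%, Kaplan-Meier standard error about 11 points;
- death 4% per year (about 7 deaths): 39.5% vs 33.1%, standard error again about 11 points.

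In no run was the Kaplan-Meier complement below the cumulative incidence.

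**The case against.** The plan promises Kaplan-Meier survival estimates of a time to event. It nowhere says it will report the complement as a proportion of patients. A death-removed curve is a defensible way to describe how durable the tolerance phenotype is. For graft loss, leaving out death with a functioning graft is a declared part of the endpoint, visible in its title: "Time to graft loss, not including death with functioning graft". Mortality is not hidden either, since it has its own curve on the same time axis and a listing. With few deaths among about 70 participants, the two estimates may be hard to tell apart.

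Most of this stands, and it rules out several stronger readings that a reader might infer:
- **That the planned primary analysis is itself biased.** It is valid for the death-removed quantity if death is independent of loss. The error lies in reading it as a patient proportion.
- **That every death is censored for graft loss.** Liver death with a non-functioning graft is an event, and the censoring of other deaths is inferred from the method.
- **That the distortion is large because the time axis runs to decades.** On the same assumed rates the gap at 20 years would be 0.8 to 16.8 points. But the schedule in Protocol Appendix 1 ends at Year 5, so only someone enrolled about 15 or more years after time zero (20 − 5) could contribute there. Eligibility sets no maximum time off immunosuppression, so this is possible, but the documents do not show that it occurs.
- **That one subset would be distorted more because it is older.** No age data are given, and SAP 7.4 makes subset analyses descriptive.

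What the objection does not remove is the gap for the real-world question. A separate mortality curve lets a reader see that deaths occurred, but it does not yield the probability of losing tolerance in the presence of death.

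**Conclusion.** The point holds as a modest improvement, not as a fault in the primary analysis. The direction is certain: read as the proportion of recipients who lose tolerance or the graft, the complement of the death-censored curve cannot be too low relative to the cumulative incidence, and it is too high once a death precedes a later loss.

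The size is unknown because no rates are documented. Under constant hazards of 1 to 5% per year for loss and 0.5 to 4% per year for death, it is about 0.1 to 2.0 points at 5 years and 0.2 to 6.4 points at 10 years. That is probably below sampling error at this sample size, but it is systematic, and the confidence interval around the Kaplan-Meier does not reflect it. It would be larger at later times only if the risk set extends that far.

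**What to change.** 1. Keep the delayed-entry Kaplan-Meier as the primary analysis. Label it death-censored, and state that its reading as loss with death removed assumes death independent of loss.
2. Under SAP 7.2.3, add the delayed-entry Aalen-Johansen cumulative incidence of loss of tolerance, with death as a competing event and a two-sided 95% confidence interval.
3. In Table 7-2, state how death is handled for graft loss. Add the same estimate there, with death with a functioning graft as the competing event.
4. Report the number of deaths before loss for each endpoint.
5. Use the cumulative incidence for any statement about the proportion losing tolerance or the graft.

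The cost is one further standard estimate per endpoint from dates already planned for collection, with no change to the primary analysis. The downside is a second curve to explain.

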### 7.2.3. Sensitivity Analyses of the Primary Endpoint

## 7.3. Secondary Endpoints

All secondary endpoints will be analyzed as described in Table 7-2.

**Table 7-2 Table of Secondary Endpoints and Analysis Methods**

Secondary Endpoint	Method	Population
Time to development of de novo anti-HLA antibody or DSA.	The time to the first de novo anti-HLA antibody or DSA be expressed in days from time zero.  Kaplan-Meier survival estimate and associated two-sided 95% confidence interval, using a delayed-entry model controlling for left-truncation of survival times through adjusting for the time from achieving operational tolerance to the time of study enrollment.	Analysis sample defined in Section 4
Time to the first episode of biopsy-proven or clinical acute rejection, steroid resistant rejection and chronic rejection.	The time to the first episode of biopsy-proven or clinical acute rejection, steroid resistant rejection or chronic rejection be expressed in days from time zero.  Kaplan-Meier survival estimate and associated two-sided 95% confidence interval, using a delayed-entry model controlling for left-truncation of survival times through adjusting for the time from achieving operational tolerance to the time of study enrollment.	Analysis sample defined in Section 4
Time to graft loss, not including death with functioning graft.	The time graft loss, not including death with functioning graft, will be expressed in days from time zero.  Kaplan-Meier survival estimate and associated two-sided 95% confidence interval, using a delayed-entry model controlling for left-truncation of survival	Analysis sample defined in Section 4

times through adjusting for the time from achieving operational tolerance to the time of study enrollment.

## 7.4. Examination of Subgroups

In addition, the following subset analyses will be performed on all study endpoints where the data permits:

- a. Allograft type (liver vs. kidney)
- b. Previous ITN study participation vs. non-ITN study referral

All subgroup analyses will be descriptive in nature.

## 7.5. Other Endpoints

The following endpoints will be examined in an exploratory nature. All analyses will be dependent upon the availability of the data.

Exploratory Endpoint	Method	Population
Time to all-cause mortality	
The time to all-cause mortality will be expressed in days from time zero.
 
Kaplan-Meier survival estimate and associated two-sided 95% confidence interval, using a delayed-entry model controlling for left-truncation of survival times through adjusting for the time from achieving operational tolerance to the time of study enrollment.
	Analysis sample defined in Section 4
Changes in renal function (defined as estimated GFR (eGFR) calculated by CKD-EPI over time in renal transplant recipients	
eGFR will be calculated using the CKD-EPI equation:
 $\text{GFR} = 141 * \min(\text{Scr}/\kappa, 1)^\alpha * \max(\text{Scr}/\kappa, 1)^{-1.209} * 0.993^{\text{Age}} * 1.018 \text{ [if female]} * 1.159 \text{ [if black]}$ 
Scr: serum creatinine (mg/dL)  <math>\kappa</math>: 0.7 for females and 0.9 for males  <math>\alpha</math>: -0.329 for females and -0.411 for males
 
All available eGFR will be displayed graphically over time in two separate ways—as absolute values and as percent change from baseline.
	Kidney transplant recipients of the analysis sample defined in Section 4
Changes in liver tests (ALT, GGT) over time in liver transplant recipients	All available ALT and GGT will be displayed graphically over time in two separate ways—as absolute values and as percent change from baseline.	Liver transplant recipients of the analysis sample defined in Section 4

Time to incidence of biliary complications in liver transplant recipients	The time to the earliest of biliary stricture requiring stenting, biliary obstruction, or cholangitis will be expressed in days from time zero.  Kaplan-Meier survival estimate and associated two-sided 95% confidence interval, using a delayed-entry model controlling for left-truncation of survival times through adjusting for the time from achieving operational tolerance to the time of study enrollment.	Liver transplant recipients of the analysis sample defined in Section 4
Incidence of diabetes or use of concomitant medications for hypertension and/or hyperlipidemia	The proportion of participants that indicate that they have been newly diagnosed with diabetes (i.e. do not have diabetes at study entry) or have recorded using a medication for hypertension and/or hyperlipidemia with a corresponding two-sided 95% exact binomial confidence interval.	Analysis sample defined in Section 4

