### **2.3 EXPLORATORY OBJECTIVE**

To assess the medical outcomes of operational tolerance over time, as determined by medical history, in allograft recipients.

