### **3.1.2 Enrollment and Accrual**

Enrollment will occur on an ongoing basis through November 1, 2020. There is no upper limit on the number of study participants, but we estimate that approximately 70 participants may be enrolled from former ITN studies and from de novo referrals. Enrollment is defined as the signing of informed consent and will be obtained prior to the initiation of any screening or study mandated procedures. Enrolled participants who do not fulfill eligibility criteria or who do not complete any mechanistic sample collection for any reason will be considered screen failures. Screening values will be considered the participant’s baseline for those who meet all eligibility criteria. If a repeat assessment is needed to confirm eligibility, the repeat value will be considered the participant’s baseline value. There is no upper limit on screen failures.

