### 3.3.4 Exploratory Endpoints

1. Time to all-cause mortality
2. Changes in renal function (defined as estimated GFR calculated for adults by CKD-EPI and for pediatric participants (< 18 years) by both CKD-EPI and modified Schwartz formulae) over time in renal transplant recipients
3. Changes in liver tests (ALT, GGT) over time in liver transplant recipients
4. Time to incidence of biliary complications in liver transplant recipients
5. Incidence of diabetes or use of concomitant medications for hypertension and/or hyperlipidemia

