## 5.2 CONCOMITANT MEDICATIONS

All immunosuppressive medications and any concomitant medications taken within 30 days prior to enrollment and to each annual visit will be documented at each visit. There are no prohibited medications.

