## 6.2 GENERAL ASSESSMENTS

### Recipient

- Informed consent
- Medical and demographic history including solid organ transplant specifics, any induction regimens, history of rejection and immunosuppression medication use since transplant:
  - For participants who previously participated in an ITN study, the participant ID and site ID (if separate) will be collected on the ALLTOL eCRF. The participant ID will be obtained by asking the ALLTOL participant for their previous ITN study participant ID and clinical study site.
- Contact information for local physician providing regular follow-up care for the kidney or liver transplant. Local care providers will be notified of any critical clinical information that may indicate allograft dysfunction. This process is further outlined in the MOP.
- Inclusion/Exclusion Criteria
- HLA and blood typing (if available)
- Change in adverse events and concomitant medications
- Development of clinical outcomes of interest, which include incidence of diabetes and/or any biliary complications

- If there is a 25% increase in the value(s) collected during the scheduled annual visit compared to the participant's baseline value, collect all liver function tests (for liver transplant recipients) or all serum creatinine levels (for kidney transplant recipients) since the last visit
- All biopsies
- All rejection episodes, including acute rejection, chronic rejection, antibody mediated rejection, and interstitial fibrosis and tubular atrophy rejection episodes

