## 4. ANALYSIS SAMPLES

The analysis sample will be comprised of all enrolled subjects that fulfill eligibility criteria and complete at least one mechanistic sample collection.

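### SAP 7.5 joins new-onset diabetes by an or to any recorded hypertension or lipid drug in one whole-sample proportion, so the figure mixes incidence with prevalence; secondarily, Table 7-2 omits the interval-censored methods that the protocol requires for the antibody endpoint

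*SAP*

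**What the plan says.** **Composite endpoint.** Protocol 3.3.4 lists as its last exploratory endpoint "Incidence of diabetes or use of concomitant medications for hypertension and/or hyperlipidemia". SAP 7.5 turns this into a single proportion with an exact binomial 95% interval. A participant counts if "newly diagnosed with diabetes (i.e. do not have diabetes at study entry) or have recorded using a medication for hypertension and/or hyperlipidemia". The population is the whole analysis sample of SAP Section 4: everyone eligible who did "complete at least one mechanistic sample collection".

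Protocol 5.2 states that "any concomitant medications taken within 30 days prior to enrollment and to each annual visit will be documented at each visit". SAP 7.1.2 adds that all data enter the analyses whatever the time of assessment. Diabetes is also collected as an outcome of its own; Protocol 6.2 lists "Development of clinical outcomes of interest, which include incidence of diabetes and/or any biliary complications". The objective served is in Protocol 2.3: "To assess the medical outcomes of operational tolerance over time, as determined by medical history, in allograft recipients".

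**Antibody endpoint.** SAP Table 7-2 states: "The time to the first de novo anti-HLA antibody or DSA be expressed in days from time zero". Its method is a delayed-entry Kaplan-Meier estimate with risk starting at study enrollment. Protocol 3.1.2 fixes that date: "Enrollment is defined as the signing of informed consent". The first serum for HLA antibodies is scheduled at Visit 0, up to 60 days later (Protocol 6.1.1), and then yearly (Appendix 1). Protocol 9.2.2 says that interval-censored methods will be used for endpoints whose exact dates are unknown. Table 7-2 does not mention them, and SAP Section 10 lists only the eGFR formula as a change.

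**The concern.** The two parts of the composite measure different things. The diabetes part is a cumulative incidence, but its denominator includes people who cannot become new cases because they already have diabetes. The drug part has no newness or timing condition. Read literally, a participant on long-standing blood-pressure treatment is a case at the first visit. The SAP does not say whether that is intended.

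Joined by an or, the parts give a number that cannot show what happened over time, which is the stated objective. No other SAP section reports them apart. The baseline characteristics in SAP 5.2 include neither diabetes nor these drugs, and SAP 8.4 shows glucose and lipid values, not diagnoses or treatment. A reader of the final report could not tell whether anyone developed diabetes or started a drug.

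The antibody row matters because it is the first listed secondary safety endpoint. With yearly samples, seroconversion is known only to lie between two visits. Kaplan-Meier needs one date, and the natural choice is the date of the positive sample, which is late. Risk also starts before any sample exists in which an antibody could be seen.

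**Working it through.** **Inputs.** N = 70 is the planning estimate in Protocol 9.3, not an achieved number. The documents give no figure for either endpoint, so there is nothing to reproduce. Every rate below is an assumption. Intervals are exact (Clopper-Pearson), the method named in SAP 7.5.

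**1. No new event at all.** If a share m takes a hypertension or lipid drug at entry, the SAP figure is m × 70 / 70.

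| Drug use at entry | SAP figure | 95% interval |
|---|---|---|
| 20% | 14/70 = 20.0% | 11.4–31.3 |
| 40% | 28/70 = 40.0% | 28.5–52.4 |
| 60% | 42/70 = 60.0% | 47.6–71.5 |

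**2. Two readings of one sentence.** Let 28 of 70 take a drug at entry, 4 of the other 42 start one, and nobody develop diabetes.
- Literal reading: (28 + 4)/70 = 32/70 = 45.7% (33.7–58.1).
- New use only, whole sample: 4/70 = 5.7% (1.6–14.0).
- New use among non-users at entry: 4/42 = 9.5% (2.7–22.6).

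**3. One value, two histories.** Let 14 participants be diabetic at entry, leaving 70 − 14 = 56 at risk.
- History A: 28 drug users at entry, no new diabetes. Composite 28/70; new onset 0/56 = 0.0% (0.0–6.4).
- History B: 14 drug users at entry, and 14 others newly diabetic and not on these drugs. Composite (14 + 14)/70 = 28/70; new onset 14/56 = 25.0% (14.4–38.4).

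**4. New diabetes does register, but only in part.** Let q = 0.20 be diabetic at entry and d = 0.10 of the rest develop diabetes, independently of drug use. New cases are (1 − q)d = 0.80 × 0.10 = 8.0% of the sample. The composite rises by (1 − m)(1 − q)d:
- m = 0.20: 0.80 × 0.08 = 6.4 points
- m = 0.40: 0.60 × 0.08 = 4.8 points
- m = 0.60: 0.40 × 0.08 = 3.2 points

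**5. Antibody row.** Simulation at N = 70. Consent is uniform over 0–5 years after Time Zero, Visit 0 is 0–60 days later, the hazard is 0.04 per year after Visit 0, and follow-up is 1–5 years. True five-year incidence: 1 − exp(−0.04 × 5) = 18.1%.

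| Analysis | Mean estimate at 5 years |
|---|---|
| Exact event dates, risk from consent | 16.7% |
| Exact event dates, risk from Visit 0 | 17.6% |
| Event dated at the detecting annual visit, risk from Visit 0 | about 12% to 13% |
| Interval-censored exponential fit | 17.7% to 18.1% |

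The start date accounts for 17.6 − 16.7 = 0.9 point. Dating at detection costs about 5 to 6 points. In the first year after entry a participant adds risk time but cannot yet have a dated event. The 12% arises when event-free participants are censored at the end of follow-up, and 13% when they are censored at their last visit. The interval-censored fit uses the model that generated the data, so its accuracy is a best case.

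**The case against.** **On the composite.** The or, and the split between incidence of diabetes and use of drugs, come from Protocol 3.3.4, so the SAP carries out the endpoint it was given. A reader might infer that counting drug use at entry is an error or a departure from the protocol. The documents do not support that: the protocol asks for use, and use at entry is use. The endpoint is the last of five exploratory ones, with no test and no decision rule. The objective is also served by mortality, eGFR, liver tests and biliary complications, and SAP 8.4 plots glucose and fasting lipids over time for everyone. All of this stands and limits the consequence to interpretation. It does not make the single figure readable, because none of those outputs counts new diabetes or new treatment.

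**On the antibody row.** A reader might go further and infer that participants positive at Visit 0 must pull the estimate down and should be removed. The documents do not support this either. Table 7-2 has no rule for them, and de novo is not defined against a particular sample. If they counted as events, the estimate would rise. The endpoint is anti-HLA antibody or DSA, so someone with non-donor antibody at Visit 0 can still develop a new DSA, and removing that person would change what is estimated. In the simulation, keeping positives (10% or 20% of the sample) with risk from consent gives about 15% or 13% to 14% only if they can never have an event. If they share the hazard of the others it gives 16.5% to 17.0%, in line with the 16.7% when nobody is positive.

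It can also be said that Protocol 9.2.2 already requires interval-censored methods, so the SAP need not repeat it. But Table 7-2 specifies a method for this row, and the two documents should agree.

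**Conclusion.** The composite point holds on the wording alone: one proportion, one interval, a newness condition on one part only, and a denominator that includes people already diabetic. How far it misleads depends on drug use at entry. With none the problem largely disappears; at 20% to 60% the figure reads 20% to 60% before anything has happened. Those rates, the N of 70 and the independence in step 4 are assumptions.

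The secondary point also holds: a method required by the protocol is missing from the SAP row and is not declared as a change. Under the assumed hazard and visit pattern, dating events at detection understates an 18.1% incidence by about 5 to 6 points, against a sampling standard deviation of about 7 points for that estimate. That size also assumes that the analyst would use the date of the positive sample, since the SAP gives no dating rule for this endpoint. The start date alone matters little, about 1 point.

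Both analyses are descriptive. The primary endpoint is not affected.

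**What to change.** **SAP 7.5, last row.** Replace the single proportion with:
- new-onset diabetes among participants without diabetes at entry;
- hypertension medication, as prevalence at entry and as new use among non-users at entry;
- lipid medication, in the same two forms;
- for the new-onset and new-use figures, the number of participants with a visit after Visit 0, because Section 4 admits people with a single collection, who cannot show a later event.

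If the composite is kept for fidelity to the protocol, state whether drugs in use at entry count and show the components beside it.

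**SAP Table 7-2, antibody row.** Apply interval-censored methods as Protocol 9.2.2 requires, naming an estimator that also handles delayed entry, or list the omission with its reason in Section 10. Start risk at the Visit 0 sample instead of at consent. Report participants positive at Visit 0 as a count, and do not remove them from the pooled endpoint.

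**Cost.** The edits touch two SAP rows and use medication, diabetes and serum data already in the schedule. The price is smaller denominators and wider intervals: if 60% take a drug at entry, 28 non-users remain, and 3 new users give 3/28 = 10.7% (2.3–28.2).
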